12.3 Data Safety Monitoring Board

An independent DSMB will be commissioned to review, on a regular basis, safety data from the study. The DSMB will advise the Sponsor regarding the continuing safety of subjects and those yet to be recruited to the study. The initial DSMB review of safety data will be conducted after five subjects have been ablated and completed the 30-day follow-up visit. Additional DSMB reviews will occur after 10 and 20 subjects have been ablated and completed the 30-day follow-up visit. After the review of the initial 20 subjects, the DSMB will determine the appropriate continued frequency for their reviews, which will continue for the duration of the study. Based on accumulating safety data from the study, the DSMB may recommend whether to continue, suspend, modify, or stop the study.

At the conclusion of the review of all enrolled and ablated subjects, the DSMB will also give a final assessment of the safety of the procedure. The composition, responsibilities, frequency of DSMB meetings, handling of emergency situations, and documentation of DSMB meetings is specified in the DSMB Charter.

Additionally, the DSMB will review all reported deaths. A report of death or severe hemorrhage requiring intervention beyond local therapy (i.e., Nashville \geq grade 2 or CTCAE \geq grade 2) within 30 days of the procedure will put enrollment on hold and require review by the DSMB to

determine if the death or hemorrhage was related to the ablation procedure. The DSMB will determine whether the study may resume enrollment or state other necessary conditions or recommendations to resume enrollment.

A document outlining membership and responsibilities will be described in detail in a separate charter, which will be finalized prior to the first subject being ablated.

13.0 PRODUCT COMPLAINT DEFINITION

A product complaint is defined as any written, electronic, or oral communication that alleges deficiencies related to the identity, labeling, quality, durability, reliability, safety, effectiveness, or performance of a device (21CFR 820.3 (b)). A product complaint may or may not be associated with an AE/SAE.

Product complaints may include, but are not limited to:

1. Product contamination;
2. Defective components;
3. Poor packaging or product mix-up;
4. Device malfunction (the failure of a device to perform as intended for this study);
5. Labeling concerns; and
6. User errors.

Reporting Product Complaints

All product complaints, malfunctions, or failures related to devices in the procedure (including both NeuWave and Auris devices) shall be documented in the Product Complaints eCRF in a timely manner after becoming aware of the event. The eCRF completion will trigger an automated notification email to the Sponsor.

The device involved in the complaint should be retained on site. A Sponsor representative will organize collection of the device for evaluation, as needed.

14.0 TRAINING

All investigators (PIs or Sub-Investigators) who will be performing the FLEX MC ablation procedure are required to undergo FLEX MC Training. The training will include lectures on microwave ablation of the lung, probe placement, margin planning and assessment, and review of cases from the previous Sponsor study on transbronchial microwave ablation using the FLEX System.²³ The training will also involve a human, simulated, or synthetic tissue lab to demonstrate the FLEX MC workflow, probe placement using augmented fluoroscopy and CBCT confirmation, scope and probe retraction workflow, and reading post-ablation CBCT images. A FLEX MC Training Completion Form will be signed upon completion of the training course and filed in the Investigator Site File.

In addition to the training, per the Investigator Selection Criteria, all investigators who will be performing the FLEX MC ablation procedure are also required to complete a minimum of 20 MONARCH diagnostic bronchoscopy procedures, with at least five of those cases using CBCT, and demonstrate proficiency prior to enrolling subjects into the trial.

The Sponsor will provide access to a Product Development Specialist and/or a Medical Specialist experienced in this procedure for the treating physician during the case, as needed. This will be mandatory for the first case at each site and may be continued at the request of the site PIs for subsequent cases.

If MONARCH is not commercially available at a site to complete the required minimum 20 diagnostic bronchoscopy procedures (with at least five of those cases using CBCT), the investigator may complete these required lead-in cases, under this protocol per the MONARCH IFU/User Manual. Subjects will consent for their diagnostic bronchoscopy as a lead-in case for this study. Lead-in cases are not treated (ablated) with the FLEX MC device at the time of the diagnostic procedure. Should the patient later qualify for the FLEX MC study, the patient will then be consented for FLEX MC study participation.

After the diagnostic bronchoscopy with MONARCH, the investigator will follow these subjects to the first follow up time point per the site's SOC (either telephone call or clinical visit), or within 7 days, to note any potential adverse events related to the diagnostic procedure, which will be reported the same way as the FLEX MC adverse events. Any data collected from these lead-in cases will be in support of appropriate event reporting.

The investigator may also perform additional "lead-in" diagnostic cases during the course of the study enrollment, if deemed warranted by the investigator to maintain proficiency with the MONARCH and/or CBCT workflow.

15.0 DATA AND PUBLICATION POLICIES

[figure not shown]
Publication and authorship policies should be determined and aligned with the clinical study agreement executed between the operating company and the clinical site. Publication of the results of this study will be governed by Johnson & Johnson publication policies, including current and applicable Medical Device Publication Policy. Any presentation, abstract, or manuscript will be made available for review by the Sponsor prior to submission. Licensing agreements or copyrights applying to tools, work products or intellectual property used during the study should be observed and clearly displayed on study documentation and publications, wherever appropriate.

All manuscripts of data obtained from this clinical study will be reviewed and approved by the Sponsor, and each author, prior to any submission. Current and applicable Medical Device Publication Policy will be followed. The Sponsor will require a written agreement for any external author(s) prior to initiating any publication. All authors must disclose financial or personal affiliations that could be considered a conflict of interest.

16.0 SUPPLEMENTS

16.1 Appendix 1: Numeric Pain Rating Scale

The Numeric Pain Rating Scale can be administered verbally (therefore also by telephone) or graphically for self-completion. Administrators will ask respondents to "indicate the numeric value on the segmented scale that best describes their pain intensity right now with 0 being NO PAIN, 5 being MODERATE PAIN, and 10 being WORST POSSIBLE PAIN".

16.2 Appendix 2: Nashville Scale for Bleeding

Grade	Findings at Bronchoscopy	Rationale
1	Suctioning of blood required for less than 1 minute	Minimal bleeding of no clinical consequence to the patient or the provider.
2	Suctioning more than 1 minute required or repeat wedging of the bronchoscope for persistent bleeding or instillation of cold saline, diluted vasoactive substances or thrombin	Requirement of one or more tools to control or prevent further bleeding.
3	Selective intubation with ETT or balloon/bronchial blocker for less than 20 minutes. Or premature interruption of the procedure.	Meaningful but short-term change in the clinical status of the patient involving more invasive procedures and causing interruption of the planned procedure.
4	Persistent selective intubation > 20 minutes or new admission to the ICU or PRBC transfusion or need for bronchial artery embolization or resuscitation.	Change in level of care and requiring advanced ventilatory support and/or transfusion of PRBC.

16.3 Glossary

Acronyms/ Abbreviations	Terms
ADL	Activities of Daily Living
AE	Adverse Event
APTT	Activated Partial Thromboplastin Time
BMI	Body Mass Index
CBC	Complete Blood Count
CBCT	Cone Beam Computed Tomography
CEA	Carcinoembryonic Antigen
CFR	Code of Federal Regulations
CO ₂	Carbon Dioxide
CT	Computed Tomography
CTCAE	Common Terminology Criteria for Adverse Events
DICOM	Digital Imaging and Communications in Medicine
DLCO	Diffusing [capacity of the] Lung [for] Carbon Monoxide
DSMB	Data Safety Monitoring Board
EBRT	External Beam Radiation Therapy
EC	Ethics Committee
ECOG	Eastern Cooperative Oncology Group
eCRF	Electronic Case Report Form
EDC	Electronic Data Capture
EKG	Electrocardiogram
ENB	Electromagnetic Navigation Bronchoscopy
EORTC	European Organization for the Research and Treatment of Cancer
EWC	Extended Working Channel
FDA	Food and Drug Administration
FEF	Forced Expiratory Flow
FEV1	Forced Expiratory Volume
FRC	Functional Residual Capacity

Acronyms/ Abbreviations	Terms
FVC	Forced Vital Capacity
GCP	Good Clinical Practice
GLP	Good Laboratory Practice
HRQOL	Health-Related Quality of Life
IB	Investigator Brochure
ICF	Informed Consent Form
ID	Identification
IDE	Investigational Device Exemption
IFU	Instructions for Use
IGTA	Image-Guided Thermal Ablation
INR	International Normalized Ratio
IRB	Institutional Review Board
LDH	Lactate Dehydrogenase
LOS	Length of Hospital Stay
LTP	Local Tumor Progression
LTPFS	Local Tumor Progression Free Survival
MDT	Multidisciplinary Team
MedDRA	Medical Dictionary for Regulatory Activities
MRI	Magnetic Resonance Imaging
MWA	Microwave Ablation
NSAID	Nonsteroidal Anti-Inflammatory Drug
NSCLC	Non-Small Cell Lung Cancer
OS	Overall Survival
PAP	Positive Airway Pressure
PDM	Power Distribution Module
PET	Positron Emission Tomography
PFS	Progression Free Survival
PFT	Pulmonary Function Test
PI	Principal Investigator
PT	Prothrombin Time

Acronyms/ Abbreviations	Terms
RAB	Robotic-Assisted Bronchoscopy
RFA	Radiofrequency Ablation
RV	Residual Volume
SAE	Serious Adverse Event
SAP	Statistical Analysis Plan
SBRT	Stereotactic Body Radiation Therapy
SOC	Standard of Care
SPO2	Oxygen Saturation
TLC	Total Leukocyte Count
UADE	Unanticipated Adverse Device Event
US	United States

## Revision History

Revision Number	Revision Date (DD/MM/YYYY)	Reasons for Revision

## Abbreviations

AE	Adverse Event
CBC	Complete Blood Count
CBCT	Cone-Beam Computed Tomography
CHF	Congested Heart Failure
COPD	Chronic Obstructive Pulmonary Disease
CRF	Case Report Form
CTCAE	Common Terminology Criteria for Adverse Events
DSMB	Data and Safety Monitoring Board
DSS	Disease Specific Survival
ECOG	Eastern Cooperative Oncology Group
FAS	Full Analysis Set
HRQOL	Health-Related Quality of Life
ITT	Intent-to-Treat
LTP	Local Tumor Progression
LTPFS	Local Tumor Progression Free Survival
MWA	MicroWave Ablation
NSCLC	Non-Small Cell Lung Cancer
OS	Overall Survival
OUS	Outside the United States
PFS	Progression Free Survival
PFTs	Pulmonary Function Tests
PI	Principle Investigator
RFA	Radio Frequency Ablation
SAE	Serious Adverse Event

## 1 Study Design

This is a prospective, multicenter, single-arm study of transbronchial microwave ablation using robotic-assisted bronchoscopy in adult subjects with oligometastatic tumors ( $\leq 2\text{cm}$ ) in the lung, located in the outer two-thirds and not closer than 1cm to the pleura (including fissures), with colorectal, renal, or sarcoma histology.

Subjects with at least one oligometastatic tumor in the lung who meet all inclusion/exclusion criteria will have transbronchial microwave ablation performed using CBCT scan for probe guidance and confirmation. Subjects will be followed for 12 months following the first ablation procedure for safety and effectiveness outcomes.

Overall, the study will include up to 145 subjects across approximately 15 sites, where principal investigators will be licensed pulmonologists/interventional pulmonologists or thoracic surgeons who have completed at least 20 diagnostic cases using the MONARCH Platform including at least 5 cases using CBCT and completed the Sponsor-required FLEX MC training.

In this study, “target” tumors are defined as lung tumors that are treated with FLEX MC at the index ablation procedure (i.e., Visit 2). A subject may have a maximum of two target tumors. “Non-target” tumors are defined as lung tumors that are treated with FLEX MC during study follow-up after completion of the primary endpoint, Technique Efficacy assessments at Visit 3 (i.e., Visits 3-6). A subject may not have more than three total tumors treated with FLEX MC (including target and non-target tumors).

A central review committee of radiologists will independently review all CT scans (and other scans, as applicable) taken throughout the clinical study in an effort to standardize scan assessment and to minimize potential bias of the treating physician. Both the clinical site’s radiographic assessment and the central review committee’s assessment will be captured within the CRFs and reported within the final Clinical Study Report. The central review committee assessment for the following key endpoints will be used for the final analysis.

Assessment	Visit 1 (Screening)	Visit 2 (Ablation Visit)	Visit 3 (30 days post-ablation)	Visit 4 (3 months post-ablation)	Visit 5 (6 months post-ablation)	Visit 6 (12 months post-ablation)
Tumor size* (smallest and largest diameters)	X					
Ablation zone (smallest and largest diameters)		X				
Smallest minimal ablation margin		X				
Technical Success		X				

Technique Efficacy			X			
Local tumor progression				X	X	X
Other tumor progression (regional or distant)				X	X	X

\*Tumor size, as analyzed by the central review committee, will be used for reporting purposes only. The investigator's assessment of tumor size will be used for inclusion/exclusion purposes.

The study will end when all enrolled and treated subjects have completed the 12-month, post-ablation follow-up period or have withdrawn consent prior to completion. The Sponsor may also stop or pause enrolling new subjects prior to reaching 145 subjects based on either safety events, regulatory feedback, or inability to enroll appropriate subjects.

Table 1: Schedule of Assessments

Visit No.	Visit 1	Visit 2			Visit 3	Visit 4	Visit 5	Visit 6	Unsched. Visit 
Visit	Screening	Pre-Procedure	Intra-Procedure	Post-Procedure	Follow-up	Follow-up	Follow-up	Follow-up	
Interval Windows	≤ 30 days pre-ablation	Day 0	Day 0	Day 0 - Discharge	30 days (-7 to +14 days)	3 months (±2 weeks)	6 months (±1 month)	12 months (±1 month)	
Standard Study Assessments									
Informed Consent	X								
Inclusion / Exclusion Criteria	X	X							
Demographics	X								
Medical / Surgical History 	X								
Concomitant medications 	X	X		X	X	X	X	X	X
Concomitant procedures	X	X		X	X	X	X	X	X
BMI	X								
Key Vitals 	X	X		X	X	X	X	X	
ECOG Status	X	X			X	X	X	X	
Pulmonary function tests (PFTs)	X					X	X	X	
Laboratory Assessments									
Pregnancy test 	X	X							
Coagulation tests 	X	X 							
CBC with differential	X								
Tumor markers/molecular profiling 	X								
Subject Report Outcome Assessments									
Numeric Pain Rating Scale	X	X		X					
Quality of Life Questionnaires 	X				X	X	X	X	
Ablation Assessments									
Ablation procedure details 		X							
Imaging Assessments									
Chest CT 	X 				X 	X	X	X	
Abdomen and Pelvis CT 	X 					X	X	X	

Visit No.	Visit 1	Visit 2			Visit 3	Visit 4	Visit 5	Visit 6	Unsched. Visit 
Visit	Screening	Pre-Procedure	Intra-Procedure	Post-Procedure	Follow-up	Follow-up	Follow-up	Follow-up	
Interval Windows	≤ 30 days pre-ablation	Day 0	Day 0	Day 0 - Discharge	30 days (-7 to +14 days)	3 months (±2 weeks)	6 months (±1 month)	12 months (±1 month)	
Imaging Assessments, Cont.									
Brain MRI 	X					X	X	X	
Extremity CT or MRI 	X					X	X	X	
Cone Beam CT			X 						
Technical Success			X						
Technique Efficacy					X				
Tumor Progression						X	X	X	
Safety Assessments									
Perioperative AEs 	X	X	X	X	X				
Other AEs						X	X	X	X
SAEs	X	X	X	X	X	X	X	X	X
Hospital-Related Assessments									
UB-04 Data 				X					
Length of hospital stay 				X					
Assess for hospital readmission 					X				

## **2 Treatment Assignment**

All subjects enrolled in this study will be treated with the transbronchial ablation procedure using the NEUWAVE™ FLEX MC Microwave Ablation System and Accessories.

## **3 Randomization and Blinding Procedures**

This is an open-label, single-arm study. No randomization or blinding of treatment will be performed.

## **4 Interval Windows**

Interval windows are provided in Table 1: Schedule of Assessments. No additional windows are planned for analysis purposes.

## **5 Levels of Significance**

The following hypotheses will be evaluated in this study:

$$H_0: p \leq 0.80 \text{ vs.}$$

$$H_1: p > 0.8$$

where  $p$  represents the true 30-day Technique Efficacy rate of FLEX MC and 0.80 is the performance goal, which was determined through an internal systematic literature review and meta-analysis of microwave and radiofrequency ablation systems used in the treatment of lung tumors.

A one-sided significance level of 0.025 will be used to test the hypotheses above. If the lower bound of the confidence interval is above 0.8, then the following secondary endpoints will be provided with 95% confidence intervals at month 12, in addition to the descriptive statistics:

- Local Tumor Progression Free Survival,
- Progression Free Survival,
- Disease Specific Survival, and
- Overall Survival

No other formal hypothesis tests are planned for this study and estimation for all other endpoints will be provided descriptively.

## 6 Analysis Sets

Intent-to-treat Set (ITT) is defined as all enrolled patients with the FLEX MC ablation procedure attempted (i.e., microwave ablation initiated). The primary analysis of effectiveness endpoints and safety will be performed on the ITT. If more than 7 patients (5%) start the ablation but fail to complete ablation due to any reasons, all the secondary efficacy analyses will also be repeated under ITT set.

Full Analysis Set (FAS) is defined as all subjects who are enrolled in the study and successfully complete the FLEX MC ablation procedure. This will be used for effectiveness endpoints.

Per Protocol analysis Set is defined as all subjects who complete the FLEX MC ablation procedure and have no major protocol deviations. Primary endpoint and Technical Success analyses will be repeated for the Per Protocol Set.

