While radiofrequency ablation (RFA) was historically the most commonly used ablative modality for percutaneous lung ablation, microwave ablation (MWA) is now the preferred option. This is largely due to MWA's ability to create larger, more uniform ablation zones in a shorter period of time as a result of MWA's improved ability to propagate through and heat high impedance lung tissue and less susceptibility to vascular "heat sinks".²² While the percutaneous approach to MWA has been more widely adopted, the transbronchial approach offers potential advantages including a lower risk of pneumothorax, bleeding, and other pleural based complications such as pleural effusion, empyema, and bronchopleural fistula. A few pilot studies have tested the feasibility of this approach.²³ The largest of these reports included 25 subjects with mixed primary non-small cell lung cancer (NSCLC) and oligometastatic lesions to the lung who were considered poor surgical candidates or opted out of surgery.²⁴ In this single center retrospective experience, 30 lesions ($\leq 3\text{cm}$) in 25 subjects were treated. Pneumothorax requiring a chest tube was reported in 2 subjects (6.7%), Grade 1 hemoptysis and an infected pleural effusion in 1 subject each. One death was reported at 12 months deemed unrelated to the procedure. During a median follow up of 1 year, no progressive disease was identified.

The Sponsor has also conducted a prospective pilot study using the NEUWAVE™ FLEX Microwave Ablation System and flexible probes in combination with electromagnetic navigational bronchoscopy (NCT03603652).²³ This study enrolled 10 subjects with primary NSCLC who either refused surgery or were deemed to be poor surgical candidates. Subjects underwent image guided ablation of their target lesion ($\leq 2\text{cm}$). The primary endpoint of technique efficacy was judged by the treating physician to have been achieved in all cases, and over 1 year of follow up, 1 subject was deemed to have had a recurrence of their disease. No pneumothoraces were reported in this study. Two subjects died during the study, 1 of which was periprocedural and was deemed to be probably related to the procedure. In this case, navigation to the lesion was prolonged and bleeding was observed during the navigation. The subject died 2 weeks later of a presumed pulmonary hemorrhage though no autopsy was performed. While the DSMB stated the study could continue

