The MONARCH Platform was first tested in a clinical feasibility study of 15 subjects.²⁸ In that study, robotic bronchoscopy to access the periphery of the lung was technically feasible, and it resulted in no serious adverse events and no procedure- or device-related complications. An additional clinical study was completed looking at the feasibility of using MONARCH in subjects (n=55) with peripheral pulmonary lesions. Results from this study showed a safety profile of the robotic-assisted bronchoscopy to be comparable with conventional transbronchial biopsy. The robotic platform successfully localized approximately 96% (51/53) of lesions, and pneumothorax was reported in 2/54 (3.7%) of cases, requiring tube thoracostomy in 1/54 (1.9%) case.²⁵ No additional adverse events were reported. In addition, the Sponsor has an ongoing 1,200 patient prospective, observational study (the TARGET study) to further characterize the diagnostic performance of the MONARCH Platform in transbronchial biopsies of pulmonary nodules (NCT04182815).

The NEUWAVE FLEX Microwave Ablation System (NeuWave Medical, Inc., Madison, WI) will be paired with the MONARCH Platform, and studied under this protocol as “FLEX MC” under an IDE issued by the FDA.

Transbronchial ablation of lung tumors will involve a physician operator using the MONARCH Platform to provide bronchoscopic visualization and access to targeted lung tumors before precisely placing the FLEX probe into the desired anatomical location manually via the working channel (lumen) of the MONARCH bronchoscope. Once the FLEX probe is precisely positioned, the physician operator can then ablate for up to several minutes until the targeted lung tissue is treated. The MONARCH Platform enables precise control and stability of a flexible bronchoscope

under continuous and direct control by a physician operator, while allowing for continuous real-time visualization of targeted lung anatomy throughout the procedure.

Conclusion

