5.2 Enrollment

Up to 145 subjects will be enrolled and ablated in this clinical study. A subject is considered to be enrolled when the ICF is signed. Enrollment will continue until up to 145 subjects have been enrolled and had the ablation procedure initiated. Participants who have the navigation initiated but do not receive the microwave ablation will either have the ablation rescheduled, pending cause, or will be considered an intra-operative withdraw/screen fail and will not count toward the 145 subjects enrolled and ablated.

If a subject experiences an adverse event (AE) after navigation and does not receive the microwave ablation, the subject should be followed from a safety perspective until the AE resolves or is deemed stable.

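### No analysis set starts at navigation, so subjects stopped in navigation and never ablated are missing from every planned adverse event rate

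*SAP*

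**What the plan says.** **Analysis sets.** SAP section 6 sets the entry point: "Intent-to-treat Set (ITT) is defined as all enrolled patients with the FLEX MC ablation procedure attempted (i.e., microwave ablation initiated". It continues: "The primary analysis of effectiveness endpoints and safety will be performed on the ITT". The SAP FAS and Per Protocol sets require a completed ablation. Protocol 10.7 defines its FAS as subjects who received ablation, and Protocol 10.9 limits all analyses to ablated subjects.

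**Stops during navigation.** Intra-operative criteria 26 to 28 in Protocol 5.4 (long navigation, bleeding, obscured imaging) can end a procedure before any energy is delivered. Under Protocol 5.2 and 5.6 such a subject is either rescheduled or "will be considered an intra-operative withdraw/screen fail and will not count toward the 145 subjects enrolled and ablated". If an adverse event has occurred, "the subject should be followed from a safety perspective until the AE resolves or is deemed stable".

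**Adverse event rates.** SAP 8.11 reports numbers and percentages of subjects, with hemorrhage of CTCAE grade 2 or higher among the events of interest. The perioperative window closes 30 days after an ablation.

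**Navigational Success.** SAP 8.8.2 promises counts and percentages but names no analysis set, unit (tumor or subject) or rule for repeat attempts.

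**ITT and FAS.** Having put effectiveness on the ITT, SAP section 6 says of the FAS: "This will be used for effectiveness endpoints". If more than 7 subjects start but do not complete ablation, "all the secondary efficacy analyses will also be repeated under ITT set".

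**The concern.** The primary objective (Protocol 4.0) covers the safety and effectiveness of FLEX MC, which combines robotic navigation with ablation. Navigation is part of what is being evaluated, yet the safety denominator opens only when microwave energy starts. The exclusion also depends on outcome: criterion 27 stops a procedure for bleeding, and if the subject is never ablated that bleed leaves the hemorrhage rate. In a single-arm study the reported rates carry the safety case. SAP 8.12 intends the second interim analysis, with its full safety summary, to support regulatory filing.

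Navigation-phase bleeding is a known concern. In the sponsor's 10-subject pilot, on a different navigation platform, one periprocedural death was judged probably related to the procedure: "In this case, navigation to the lesion was prolonged and bleeding was observed during the navigation".

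Two smaller issues sit beside this. If Navigational Success is computed on ablated subjects, it cannot register the failures it is named for. And the ITT and FAS wording leaves open whether subjects who start but do not complete ablation count in Technical Success.

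**Working it through.** **1. Sample size (not in dispute).** SAP section 7 uses rates of 0.80 and 0.90, one-sided alpha 0.025 and power above 90%.

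n = [(1.960·√(0.8·0.2) + 1.282·√(0.9·0.1)) / 0.10]² = 136.5, so 137, with power 90.1%. Then 137/0.95 = 144.2, so 145. Both figures reproduce. Because 145 counts ablated subjects, a set starting at navigation does not change it.

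**2. Tracing one subject.** Consent is signed and navigation starts. Bleeding meets criterion 27, the procedure stops, and no re-attempt follows.

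| Set | Entry requires | Included? |
|---|---|---|
| SAP ITT | ablation started | No |
| SAP FAS | ablation completed | No |
| SAP Per Protocol | ablation completed, no major deviation | No |
| Protocol FAS | ablation received | No |
| Protocol Per Protocol | ablation undergone, no major deviation | No |

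The perioperative window has no end date for this subject, since no ablation occurred. The SAE window runs to study end or discontinuation and does not have that problem.

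**3. Scale for k, the navigated but never ablated subjects.** The documents give no k. The nearest anchor is in Protocol 3.0: "The robotic platform successfully localized approximately 96% (51/53) of lesions". 51/53 = 96.2%, Wilson 95% CI 87.2% to 99.0%. For 145 ablated one-tumor subjects, first-attempt localization failures = 145/p − 145:
- p = 96.2%: 5.7
- p = 99.0%: 1.5
- p = 87.2%: 21.2

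This is a scale, not an estimate of k. The cited study was diagnostic and re-attempts are allowed here, which lowers k; stops for bleeding could raise it.

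**4. Effect on the rates.** Assume one tumor per subject, every ablated subject a navigational success, and 5 qualifying hemorrhages among 145 ablated (5/145 = 3.4%).

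| k | Navigational Success, 145/(145+k) | Hemorrhage if none of k bled, 5/(145+k) | Hemorrhage if all k bled, (5+k)/(145+k) |
|---|---|---|---|
| 0 | 100.0% | 3.4% | 3.4% |
| 1 | 99.3% | 3.4% | 4.1% |
| 3 | 98.0% | 3.4% | 5.4% |
| 6 | 96.0% | 3.3% | 7.3% |
| 15 | 90.6% | 3.1% | 12.5% |

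**5. Technical Success, ITT or FAS.** Assume 131/145 = 90.3% on the ITT and 7 non-completers, the most allowed without triggering the repeat. If s of the 7 are classed A0 or A1, the FAS rate is (131 − s)/138:
- s = 0: 94.9%
- s = 3: 92.8%
- s = 7: 89.9%

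The direction is not fixed.

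**The case against.** The strongest reply is that little is lost.

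- **The events are captured.** Adverse event pages are completed for screen failures (Protocol 5.6), the phase of each event is recorded (12.2), subject listings are planned (SAP 8.1), and the DSMB reviews deaths and severe hemorrhage (Protocol 12.3, SAP section 9). This stands. The gap is in the reported rates, not in collection or oversight, but listings and DSMB review do not supply a rate.
- **k may be zero.** Notes 1 to 3 of Protocol 5.4 allow re-attempts, and subjects later ablated enter the ITT. This also stands. Re-attempts are optional, however, and Protocol 5.2 and 5.6 provide expressly for subjects who are never ablated.
- **The pilot death does not demonstrate the gap.** Protocol 3.0 says the pilot subjects underwent ablation, with technique efficacy judged achieved in every case, so that subject would apparently be in this ITT. That is right. The pilot shows that navigation bleeding matters; that criteria 26 and 27 could stop a similar course before ablation is inference.
- **The upper hemorrhage bounds are extreme.** They need every stopped subject to bleed, and the study behind 51/53 reported pneumothorax but no other adverse events. They should be read as bounds only.
- **Navigational Success need not be 100%.** If failed first attempts count as failures, or a second planned tumor is not reached, the rate falls. That is so, and the SAP does not say which rule applies.

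Protocol 5.6 itself is inconsistent. Its first paragraph equates initiating the procedure with starting navigation, so a navigated subject is not a screen failure on that ground; its second paragraph allows that classification. The SAP ties an attempted procedure to starting microwave energy.

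**Conclusion.** The concern holds and should be fixed. Confidence in the reading of the text is high: a subject stopped in navigation and never ablated enters no planned adverse event rate, and the reason for the stop can be the event being measured.

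The size is illustrative because k is unknown. At k = 6, an assumed 3.4% hemorrhage rate becomes 3.3% to 7.3%, and Navigational Success becomes 96.0% instead of 100%; at k = 0 nothing changes. Navigational Success is biased upward only if the ablated sets are used as its denominator.

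The ITT and FAS wording is a secondary clarification. The protocol's FAS essentially matches the SAP's ITT, while the SAP reuses the FAS label for completers. The affected endpoints are descriptive. The hypothesis test on Technique Efficacy and the 137/145 sample size stand.

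**What to change.** Make these changes before the analysis that supports filing, and in any case before database lock:

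1. Define a Safety Set of all subjects in whom study navigation was started with intent to ablate, with the diagnostic lead-in cases of Protocol 14.0 kept separate. Use it for the adverse event tables, split by the recorded phase of the event, and show ITT rates alongside. For never-ablated subjects, anchor the perioperative reporting window to the navigation attempt.
2. Analyse Navigational Success on all planned tumors with navigation attempted. State the unit and how a failed first attempt followed by a successful one is counted.
3. Name the ITT as the set for Technical Success and the other secondary effectiveness endpoints, without the trigger of more than 7 non-completers, and keep the completers' set as supportive. Score incomplete procedures by their CBCT classification and state how those without an assessable CBCT are handled.
4. Reconcile the FAS label between Protocol 10.7 and SAP section 6, and the meaning of an initiated procedure between Protocol 5.6 and the SAP.

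The cost is wording in both documents plus a few navigation fields for non-ablated subjects; their adverse event pages and the phase field already exist. Reported hemorrhage and Navigational Success rates may look less favourable. Ablation-specific rates would be slightly diluted: with an assumed 10 events and k = 6, 10/145 = 6.9% becomes 10/151 = 6.6%. Showing both denominators deals with that. No clinical stopping criterion needs to change.
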